3.3 Tertiary/Exploratory/Correlative Outcome Measures

Specific Aim 3:

Serum mirabegron metabolites will be used to determine the mirabegron metabolism using metabolomics.

Body composition will be measured using DEXA once after informed consent during the screening visit. We will run exploratory correlational analyses among the other physiological data collected and body composition.

4.0 Eligibility Criteria

4.1 Inclusion Criteria

List the criteria:

- Men and women
- 18-40 years old
- Participate in 150 minutes or more of at least moderate intensity exercise per week during the previous 2 years

4.2 Exclusion Criteria

List the criteria:

- Any autonomic cardiovascular, metabolic, neurologic, endocrine, or respiratory disease
- Previously diagnosed liver and/or kidney dysfunction
- Women who are pregnant or breastfeeding
- Individuals currently taking a medication that cannot be safely discontinued for 5 biological half-lives prior to each study visit based on consultation with the study physician. Birth control (including hormonal contraception) will be permitted despite potential to influence vasomotor activity.
 - Increases in heart rate and blood pressure are common with the higher doses of mirabegron that we will be testing. Additionally, medications that influence vasomotor activity may also influence thermoregulation.
- Therefore, for participant safety, we do not want to study participants that are taking a medication that might interfere with our ability to properly monitor and interpret the potential side effects of mirabegron during cold exposure.
- Current tobacco or electronic cigarette use or consistent use within the last 1 year

5.0 Study Design

Specific Aim 1: This is a randomized, double-blind, placebo-controlled, cross-over experimental design. Participants will be asked to complete 5 visits to the laboratory; one informed consent/screening visit and 4 study visits. During the informed consent/screening visit, participants will complete the informed consent, eligibility criteria will be presented, resting blood pressure and heart rate (derived from the blood pressure measurement) will be measured, and participants will complete the following questionnaires: iPAQ, PAR-Q, and Health

History Questionnaire. During the study visits, participants will undergo baseline measurements (described in detail in Section 7.0) followed by ingesting either a placebo or 3 different doses of mirabegron (100 mg, 150 mg, or 200 mg). Mirabegron will be prescribed by our study physician, [name]. [name] is a physician in the Department of Emergency Medicine at Indiana University Health and he is a Fellow in Wilderness Medicine through the Wilderness Medical Society as well as a member of the Indiana Task Force 1 (part of the FEMA Urban Search and Rescue System. [name] will determine if it is safe for a potential participant to stop their medication for 5 half-lives during screening. [name] will also review health history, resting heart rate and blood pressure measurements, and contraindications for mirabegron use to determine eligibility. A second set of baseline measurements will be made prior to participants entering our whole-body indirect calorimeter set at 20°C (68°F) for 6 hours. Every 30 minutes in the chamber, participants will be asked to assume the supine position to record resting energy expenditure (i.e., thermogenesis) and other physiological variables (described in detail in Section 7.0). This design will allow us to determine which dose of mirabegron produces the greatest increase in thermogenesis.

Informed Consent/Screening Visit: Obtain informed consent. Screen potential participants by inclusion and exclusion criteria. Obtain Health History Questionnaire, PAR-Q+, and IPAQ and resting heart rate and blood pressure. Perform body composition assessment with DEXA.

Study Visits 1-4

The order of placebo and mirabegron doses (100 mg, 150 mg, and 200 mg) will be randomized among Study Visits 1-4. All study procedures will be identical between Study Visits.

For specific study protocol and data collection procedures, please see Sections 7.0 and 8.0.

Specific Aim 2: This is a randomized, double-blind, placebo-controlled, cross-over experimental design. Participants will be asked to complete 3 visits to the laboratory; one informed consent/screening visit and 2 study visits. During the informed consent/screening visit, participants will complete the informed consent, eligibility criteria will be presented, resting blood pressure and heart rate (derived from the blood pressure measurement) will be measured, and participants will complete the following questionnaires: IPAQ, PAR-Q, and Health History Questionnaire. During the study visits, participants will undergo baseline measurements (described in detail in Section 7.0) followed by ingesting either a placebo or one dose of mirabegron (100 mg) prior to entering our water immersion tank. Mirabegron will be prescribed by our study physician, [name] (Department of Emergency Medicine, Indiana University Health). The dose of mirabegron that will be used for Specific Aim 2 is dependent on our findings from Specific Aim 1. The dose of mirabegron that elicits the greatest increase in thermogenesis in Specific Aim 1 will be used for Specific Aim 2. A second set of baseline measurements will be made and then the water immersion tank will then be rapidly filled with 35°C (95°F) water. The temperature of the water will be progressively lowered by ~12°C every 60 minutes until the water temperature reaches 10°C (50°F) or until the participant can no longer tolerate the cold or if rectal temperature reaches 35.5°C (95.9°F). Participants will be continuously monitored for rectal temperature, indices of shivering, skin temperature, heart

rate, blood pressure, and thermal perceptions (described in detail in Section 7.0). This design will allow us to determine if mirabegron improves cold water immersion tolerance.

Informed Consent/Screening Visit: Obtain informed consent. Screen potential participants by inclusion and exclusion criteria. Obtain Health History Questionnaire, PAR-Q+, and IPAQ and resting heart rate and blood pressure. Perform body composition assessment with DEXA.

Study Visits 1-2
 The order of placebo and mirabegron (100 mg) will be randomized between Study Visits 1-2. All study procedures will be identical between Study Visits. For specific study protocol and data collection procedures, please see Sections 7.0 and 8.0

Specific Aim 3: This aim will be addressed using the study design and visits used for Specific Aim 1 (a randomized, double-blind, placebo-controlled, cross-over experimental design). During these study visits, we will collect whole blood at pre-mirabegron/placebo and 15 minutes post the 6 h protocol. The whole blood will be allowed to clot and we will obtain serum samples for analyses. Participants will also be given fecal sample collection kits that they will take home to be used to collect fecal samples from their first bowel movement following each study visit. The serum and fecal samples will be sent to a colleague at Rutgers University for analyses. All samples will be de-identified prior to being sent to Rutgers University.

6.0 Enrollment/Randomization

We plan to recruit 60 total participants for this project (30 for Specific Aim 1 and 30 for Specific Aim 2). Participants who partake in Specific Aim 1 will also be used for Specific Aim 3 and can participate in Specific Aim 2. Two informed consent forms will be used for Specific Aim 1 & 3 (Mirabegron and Thermogenesis in Cold Air) and Specific Aim 2 (Mirabegron and Thermogenesis in Cold Water).

Participants will be recruited from the IU student body and local citizen population through flyers placed around campus, announcements made to classes of students, and word of mouth. Participants who are interested will contact the principal investigator or IRB approved personnel by email or by phone. This population may include IU students and individuals outside the IU community.

Potential participants will be given the basic information about the study and schedule an appointment for screening if they indicate that they would be interested in participating. Participants will be provided with detailed description of study procedures prior to study enrollment. Participants will be asked to read the consent form at this time and encouraged to ask any questions. Participants can then: 1) sign the consent form; 2) take it home for further consideration; or 3) decide not to participate. Participants will be screened once written informed consent has been given.

Both Specific Aim 1 (& 3) and Specific Aim 2 study visits will be completed in a randomized order. Randomization of the order of the study visits will be completed by a research technician using a

randomization list that will be created by a trained statistician external to the research team using R (R Foundation for Statistical Computing, Vienna, Austria) and our subjects will be randomized by our research technician.

7.0 Study Procedures

All of the below mentioned procedures are being conducted for purposes of the research.

- Height: Body height will be measured using a stadiometer.
- Weight: Weight will be measured using a scale in a private room.
- Pregnancy test: To ensure female participants are not pregnant they will undertake a urine pregnancy test during screening and before each study visit.
- Urine Specific Gravity: A sample of urine will be used to assess urine specific gravity using a refractometer.
- Heart rate: Heart rate will be obtained using a 3-lead electrocardiogram.
- Arm Blood Pressure: Blood pressure will be monitored using a cuff placed on the upper arm that is inflated and deflated periodically. Blood pressure measurements will be taken at several different time points. Heart rate will also be derived from this measure during the informed consent/screening visit. Each measurement will last approximately 30 seconds.
- Arterial Oxygen Saturation: Pulse oximetry will be used at the forehead to obtain continuous arterial oxygen saturation values.
- Partial Pressure of End Tidal CO₂: A nafion tube will be connected to a small port in the mouthpiece to measure end tidal partial pressure of CO₂.
- Ventilation: A pneumotach connected to a mouthpiece or facemask will be used to measure the flow of inspired and expired air. Expired gases will be sampled using oxygen and carbon dioxide sensors to determine oxygen consumption and carbon dioxide production.
- Core temperature: Participants will self-insert a single use rectal temperature probe in a private room. A small (~3 mm in diameter), single use, lubricated, flexible probe will be inserted by the participant to a pre-marked depth of ~10 cm.
- Skin Temperature: Fourteen iButtons will be adhered to the skin using adhesive tape on the calf, shin, front thigh, back thigh, foot, chest, upper back, lower back, forearm, hand, forehead, fingertip, toetip, and abdomen area to measure skin temperature.
- Perceptual Scales: Participants will complete Likert scales to assess their thermal comfort (1 = comfortable, 4 = very uncomfortable) and thermal sensation (1 = cold, 4 = neutral, 7 = hot).

- Bedside Shivering Scale: Two investigators will subjectively assess shivering by the participants using a Likert scale (0 = none, 3 = Severe) and the scores will be averaged.
- Surface Mechanomyography: Three triaxial accelerometers adhered to the skin using adhesive tape on the chest, upper back, and thigh will be used to assess shivering.
- Resting Energy Expenditure (thermogenesis): Expired oxygen, carbon dioxide, and ventilation will be collected from the whole-body calorimetry and used to calculate thermogenesis using the abbreviated Weir formula (5).
- International Physical Activity Questionnaire: Participants will complete this form to self-report and quantify their level of physical activity.
- Health history and demographics questionnaire: Participants will complete a health history questionnaire to ensure they meet the inclusion and exclusion criteria.
- Health history update questionnaire: Upon each visit to the laboratory participants will complete the health history update questionnaire to ensure no changes in their health history has occurred.
- Infrared Thermography Images: An infrared thermography camera will be used to measure skin temperature in the supraclavicular (i.e., collar bone) region. This provides a non-invasive estimate of brown adipose tissue activation (6).
- PAR-Q+: Participants will complete this questionnaire to ensure they meet the inclusion and exclusion criteria.
- 3-Day Dietary Log: Myfitnesspal.com (Under Armour) is a dietary log that will be used to quantify the type and amount of food and fluid that participants consume 3 days prior to each study visit.
- Body Composition: Participants will have their body composition measured using DEXA.
- Whole Blood Collection: 15 mL of whole blood will be obtained from an antecubital vein at pre-mirabegron/placebo and at 15 minutes post protocol using standard aseptic techniques defined by the World Health Organization.
- Fecal Sample Collection: Participants will be given fecal collection kits (DNA Genotek) and will be given verbal instructions from the collection kit directions on how to obtain samples as well as the pamphlet that contains these directions the after the study visits of Specific Aim 1. Participants will be instructed to obtain samples from their first bowel movement after each study visit.

Timeline of Procedures

Specific Aim 1

- Informed Consent/Screening Visit: Once participants arrive at the laboratory, an investigator will obtain written informed consent after all procedures and study risks are fully explained and all questions answered. After obtaining written informed consent, participants will complete a Health History and Demographics Questionnaire, an International Physical Activity Questionnaire (IPAQ), Physical Activity Readiness Questionnaire (PAR-Q+). An experienced investigator will administer these questionnaires. These individuals can fully explain any technical terms and answer any inquiries related to the questionnaire. A resting heart rate and arm blood pressure measurement will be done after the questionnaires are complete. Participants will then have their body composition measured using DEXA. If DEXA cannot be performed during this visit, an additional visit can be scheduled. Participants will also visit with [name] to review medical history and resting blood pressure and heart rate measurements to review any contraindications for taking mirabegron. The visit with [name] can be in person or through a scheduled Zoom call to reduce participant scheduling burden. In the case of a Zoom call, [name] will be provided the medical history and resting blood pressure and heart rate measurements prior to the call.
- Study Visits: Mirabegron has a half-life of ~50 hours so all study visits will be separated by at least a 10-day washout period. Our goal will be to have 10-14 days in between study visits. Participants will report to the temperature and humidity-controlled laboratory in the morning following a 12-hour fast, and 24-hour abstention from exercise, caffeine, and alcohol. Participants will bring their dietary logs for review to ensure a consistent diet prior to each study visit. Participants will consume a light standard breakfast (237 ml Ensure Original; 220 kcal) upon arrival and be instrumented for skin temperature (12-sites: calf, shin, front of the thigh, back of the thigh, chest, upper back, forehead, lower back, abdomen, forearm, hand, and foot; iButtons) core temperature (rectal thermistor), indices of shivering (surface mechanomyography using triaxial accelerometers at 3 anatomic sites (chest, upper back, and thigh) and the bedside shivering assessment scale), brachial artery blood pressure (brachial artery auscultation), and heart rate (3-lead ECG). Thermal perceptions will be assessed using Likert scales for thermal discomfort and thermal sensation. Participants will be shirtless (sports bra for women) and will wear shorts throughout the study. After 20 minutes of quiet resting in the supine position, 5 minutes of baseline measurements will be taken, thermal perceptions and an infrared thermography image of the supraclavicular fossa will be obtained as an indicator of brown adipose tissue activation (6), and a whole blood sample will be obtained. Whole blood samples will be allowed to clot at room temperature (~15-30 minutes). The clot will be removed via centrifuging the samples at 1,500 g for 10 minutes. The serum samples will then be frozen (-80°C) until they are shipped on dry ice to Rutgers University for analysis. Participants will then ingest mirabegron (100 mg, 150 mg, or 200 mg) or placebo. Thirty minutes after mirabegron or placebo has been ingested, participants will enter the whole-body indirect calorimeter; the internal temperature of the calorimeter will be set to 20°C (68°F). This will elicit a mild cold stress over the 6 hours of observation in the whole-body indirect calorimeter. The whole-body indirect calorimeter provides an accurate and continuous measure of thermogenesis (in the form of energy expenditure) that can be used over

long periods of time in a stable environment. Our whole-body calorimeter is designed to perform human studies that are up to 48 hours in duration and contains a private washroom. While in the whole-body indirect calorimeter, participants will be instructed to be sedentary and will be allowed to watch television or read. In order to stay consistent between study visits, participants will be instructed to spend the same amount of time watching television or reading for each study visit. Every 30 minutes, we will record skin temperatures, core temperature, blood pressure, and heart rate. Thermogenesis will be determined by having participants lie supine for 30 minutes and resting energy expenditure will be calculated using the abbreviated Weir formula every hour (5). Thermal perceptions and an infrared thermography image will also be obtained at these time points. At approximately the midpoint of the 6-hour measurement period, participants will have the opportunity to use the restroom and an additional urine sample will be collected at this time. At the end of the 6-hour measurement period, participants will exit the whole-body indirect calorimeter and final measurements of skin temperature, core temperature, heart rate, and blood pressure will be obtained as well as a final infrared thermography image and a whole blood sample. After the study, participants will be given a mylar blanket to re-warm themselves prior to leaving the laboratory. Participants will be given a fecal collection kit that they will take with them. Instructions will be provided (both verbal and written) on the proper handling of their sample. If participants complete the informed consent/screening visit and all study visits, we expect that they will spend a total of ~33 hours in the study.

Specific Aim 2

- Informed Consent/Screening Visit: Once participants arrive at the laboratory, an investigator will obtain written informed consent after all procedures and study risks are fully explained and all questions answered. After obtaining written informed consent, participants will complete a Health History and Demographics Questionnaire, an International Physical Activity Questionnaire (IPAQ), Physical Activity Readiness Questionnaire (PAR-Q+). An experienced investigator will administer these questionnaires. These individuals can fully explain any technical terms and answer any inquiries related to the questionnaire. A resting heart rate and arm blood pressure measurement will be done after the questionnaires are complete. Participants will then have their body composition measured using DEXA. If DEXA cannot be performed during this visit, an additional visit can be scheduled. Participants will also visit with [name] to review medical history and resting blood pressure and heart rate measurements to review any contraindications for taking mirabegron. The visit with [name] can be in person or through a scheduled Zoom call to reduce participant scheduling burden. In the case of a Zoom call, [name] will be provided the medical history and resting blood pressure and heart rate measurements prior to the call.
- Study Visits: Mirabegron has a half-life of ~50 hours so all study visits will be separated by at least a 10-day washout period. Our goal will be to have 10-14 days in between study visits. Participants will report to the temperature and humidity-controlled laboratory in the morning following a 12-hour fast, and 24-hour abstention from exercise, caffeine, and alcohol. Participants will bring their dietary logs for review to ensure a consistent diet prior to each study visit. On arrival, participants will provide a urine sample to ensure they are hydrated via urine specific gravity. Participants will consume a light standard breakfast (237 ml Ensure Original; 220 kcal) and enter the

empty water immersion tank. Then they will be instrumented for the measurement of heart rate (3-lead ECG), blood pressure (brachial artery auscultation), core temperature (rectal thermistor), and indices of shivering (surface mechanomyography using triaxial accelerometers at 3 anatomic sites (chest, upper back, and thigh), oxygen consumption via ventilation and expired gases, and the bedside shivering assessment scale). Thermal perceptions will be assessed using Likert scales for thermal discomfort and thermal sensation. Following 10 minutes of resting baseline measurements, infrared thermography will then be used to measure skin temperature of the supraclavicular fossa as an estimate of brown adipose tissue activation and thermal perceptions will be assessed. The participants will then ingest either mirabegron (100 mg) or a placebo tablet. The dose of mirabegron will be determined from the results of Specific Aim 1. The dose of mirabegron that elicits the greatest increase in thermogenesis in Specific Aim 1 will be used in Specific Aim 2. The measurement of supraclavicular fossa skin temperature (infrared thermography) and thermal perceptions will be assessed every 10 minutes prior to the progressive cold-water challenge. After 30 minutes of seated rest, pre-immersion measurements of heart rate, blood pressure, core temperature, shivering, and thermal perceptions will be conducted and an infrared thermography image will be taken. Then, the water immersion tank will be filled up to the participant's neck with 35°C (95°F) water. Heart rate, blood pressure, core temperature, and shivering indices will be continuously measured. Infrared thermography and thermal perceptions will be obtained every 5 minutes throughout the progressive cold-water challenge. The water will be cooled at a rate of 12°C per hour until the water temperature reaches 10°C (50°F), the participant can no longer tolerate the cold water, or core temperature reaches 35.5°C (95.9°F). This is 0.5°C higher than the clinical definition of hypothermia. Also, the risks associated with hypothermia are core body temperature-dependent and not dependent on time (7). Upon completion of the progressive cold water challenge, the water in the tank will be rapidly emptied. Participants will gently towel dry and will be able to don a circulating warm water perfused suit and/or use a mylar blanket to reestablish core temperature. If participants complete the informed consent/screening visit and all study visits, we expect that they will spend a total of ~11 hours in the study.

Specific Aim 3

The serum and fecal samples that were obtained during the study visits for Specific Aim 1 will be used for the Specific Aim 3. Serum samples will be frozen at -80°C until they are shipped on dry ice to Rutgers University for analyses. Participants will be given the option to directly send their fecal samples to Rutgers University (shipping will be paid for by the study) or they can bring their samples in to the lab and a staff member will ship the samples to Rutgers University. All samples will be de-identified.

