- Acute Mirabegron ingestion: Mirabegron ingestion in the population that will be studied is deemed safe (3) and will be prescribed under the direction of our study physician, [name]. The doses that will be used in this study have mild cardiovascular (heart rate and blood pressure) effects that are associated with the dose of mirabegron (e.g., the greater the dose of mirabegron, the greater the cardiovascular response (2, 3). Acute oral administration of 200 mg of mirabegron has been shown to increase heart rate by ~8 beats per minute and systolic blood pressure by ~10 mmHg with no changes in diastolic blood pressure (2). These increases in heart rate and blood pressure are far below the heart rate and blood pressure

responses associated with moderate to heavy exercise intensities that are achieved in healthy 18-40 year old men and women.

- Head Out Water Immersion: Water temperature during Specific Aim 2 will be perceived as being cold and rectal temperature will decrease and participants might shiver. We will constantly monitor rectal temperature during the study visits for Specific Aim 2. Any risks are reversible with removal from the cold water and warming with warm water perfused suits and/or mylar blankets, which are located in the laboratory. The protocol will be immediately terminated if core temperature drops to 35.5°C or if the participant does not want to continue. This safety cutoff is 0.5°C higher than the clinical definition of hypothermia and we don't expect core temperature to drop to 35.5°C. For instance, 60 minutes of 15°C water immersion decreased core temperature less than 1°C (8). Another study safely had participants sit in 10°C (50°F) water up to the mid-sternum for 90 minutes and core temperature only decreased to 36.2°C (9). In a case study, 88 minutes of full body immersion in crushed ice lowered core temperature from 37.6°C to 37.0°C (10). Also, the risks associated with hypothermia are core body temperature-dependent and do not appear to be dependent on time (7).
- Whole blood sample: Participants will likely experience discomfort during venous blood draws and in rare circumstances may feel lightheaded or faint. This risk will be minimized by the venipuncture always occurring in the semi-recumbent or supine position. There is a rare risk of infection following venous blood draws. This risk will be minimized by blood draws only being conducted by trained laboratory personnel.

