12.0 Statistical Considerations

Specific Aim 1

Power Analysis: Using data from Loh et al. (2) we expect to observe an effect size (δ) of 0.90 for the comparison of resting energy expenditure in the placebo condition versus 200 mg of mirabegron. Given this effect size, 10 participants will be needed to achieve a power of 0.99 with an alpha level set at 0.05. To account for possible attrition, we plan on recruiting up to 30 participants.

Statistical Approach: We will compare the primary (i.e., thermogenesis) and secondary (i.e., core temperature, skin temperature, heart rate, blood pressure, indices of shivering, thermal perceptions, and infrared thermography images) dependent variables using mixed effects ANOVA (i.e., mirabegron dose x time) followed by Tukey's post hoc procedure if a significant interaction or main effect is found from the ANOVA analyses. We will also calculate the thermogenesis area under the curve for each dose of mirabegron. These values will be compared using repeated measures ANOVA followed by Tukey's post hoc procedure if a significant main effect is found from the ANOVA analysis. We will also perform correlation analyses to determine the relation between body composition and our primary and secondary dependent variables. The alpha level will be set at $P < 0.05$ for all analyses.

Specific Aim 2

Power Analysis: Similar to Specific Aim 1 and the data from Loh et al. (2), we expect to observe an effect size (δ) of 0.90 for the comparison of rectal temperature in the placebo condition versus the mirabegron condition. Given this effect size, 10 participants will be needed to achieve a power of 0.99 with an alpha level set at 0.05. To account for possible attrition, we plan on recruiting up to 30 participants.

Statistical Approach: The primary (i.e., core temperature deflection point) and secondary (i.e., onset of shivering inflection point) dependent variables from the mirabegron and placebo trials will be compared using paired t-tests to determine if mirabegron improves cold-water immersion tolerance. Mixed effects ANOVA will be used to compare the remaining dependent variables between conditions (i.e., mirabegron vs. placebo) and across time. If a significant

interaction or main effect results from the ANOVA analyses, we will use the Holm-Sidak post hoc test to determine where differences exist. The alpha level will be set at $P < 0.05$ for all analyses.

Specific Aim 3

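### In Aim 2 the thermal sensation scale ends at cold, so ratings risk a floor late in the cooling challenge that could hide or shrink a drug-placebo difference there

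*Combined protocol and SAP*

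**What the plan says.** Section 7.0 (Perceptual Scales) anchors the seven-point sensation rating as follows: "thermal sensation (1 = cold, 4 = neutral, 7 = hot"). Cold is its lowest category. Comfort is rated separately on four points, the worst of which is very uncomfortable.

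For Aim 2, the study-visit timeline in Section 7.0 says that "the water immersion tank will be filled up to the participant's neck with 35°C (95°F) water". From there the temperature is lowered by 12°C each hour to an endpoint of 10°C. Immersion ends sooner if the volunteer finds the cold intolerable or if rectal temperature falls to 35.5°C. On the timing of the ratings the plan states: "Infrared thermography and thermal perceptions will be obtained every 5 minutes throughout the progressive cold-water challenge".

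Section 9.0 (Head Out Water Immersion) describes the expected experience: "Water temperature during Specific Aim 2 will be perceived as being cold and rectal temperature will decrease and participants might shiver".

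Section 12.0 (Specific Aim 2) tests the core temperature deflection point and the shivering inflection point by paired t-tests. The rule for all other outcomes reads: "Mixed effects ANOVA will be used to compare the remaining dependent variables between conditions". Time is the second factor in that model. Thermal perceptions fall in this last group. Nothing in the section deals with ratings at the end of a scale.

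**The concern.** The word that Section 9.0 uses for the expected sensation is also the bottom anchor of the rating scale, yet the water may go on cooling to 10°C. Once a participant rates 1, the scale cannot record any further worsening. If both visits are at 1 at the same time point, the recorded difference is zero whatever the participant feels.

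Two consequences follow for the ANOVA on raw ratings. The average difference between conditions is pulled towards zero. In addition, a benefit that is constant throughout would be recorded in full early on and then shrink, producing a condition by time interaction that comes from the scale.

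This matters because Section 1.0 gives thermal comfort in cold water as part of the reason for the trial, and Section 5.0 lists thermal perceptions among the Aim 2 measurements in a design meant to judge immersion tolerance. A report that the drug brings no perceptual benefit in the coldest water could be a product of the rating card.

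**Working it through.** The plan states no figure on this point, so there is none to reproduce.

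**Inputs from the documents.** Start 35°C, end 10°C, cooling 12°C per hour, ratings every 5 minutes (Section 7.0, Aim 2 study visits); sensation scale 1 to 7 with 4 neutral and 1 cold (Section 7.0, Perceptual Scales).

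**Length of the challenge.**
- Full duration: (35 − 10)/12 h = 25/12 h = 125 min.
- Ratings: 125/5 + 1 = 26 per visit.
- Water temperature change between ratings: 12 × 5/60 = 1°C.

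**Share of a completed challenge in water colder than the point where 1 is reached.** If that point is T, the share is (T − 10)/25: 72% for 28°C, 60% for 25°C, 48% for 22°C, 40% for 20°C, 20% for 15°C and 0% for 10°C. Early stopping would reduce these shares. T is not in the documents, so the whole range is shown.

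**Simulation of the effect on the ratings.** Assumptions, none of them from the documents: mean underlying sensation on placebo falls linearly from 4 at 35°C to 1 at T and continues at the same slope; between-person SD 0.6, between-visit SD 0.35, single-reading SD 0.3; constant drug benefit 0.5 points; ratings rounded to whole numbers and cut at 1 and 7; 10 participants, all completing both visits; 4,000 replicates. Understatement = 1 − (observed mean difference)/0.5.

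| Assumed T | Mean difference over the challenge | Understated by about | Difference at 15°C | Difference at 10°C |
|---|---|---|---|---|
| 28°C | 0.16 | 69% | 0 | 0 |
| 25°C | 0.22 | 56% | 0 | 0 |
| 22°C | 0.28 | 44% | 0.01 | 0 |
| 20°C | 0.32 | 35% | 0.07 | about 0 |
| 15°C | 0.41 | 17% | 0.32 | 0.12 |
| 10°C | 0.47 | 7% | 0.44 | 0.32 |

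Percentages come from unrounded means and move by about one point between runs. In the first 25 minutes the observed difference is about 0.5 in every row, so a constant benefit is recorded as one that declines.

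**Second check with other assumptions.** With 30 pairs, between-person SD 0.7 and within-person SD 0.5, a paired t-test on the single reading at 10°C gave:

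| Assumed T | Placebo ratings at 1 | Observed difference, true 0.5 / 1.0 | Power, true 0.5 / 1.0 |
|---|---|---|---|
| 25°C | 100% | 0.00 / 0.00 | 0.00 / 0.00 |
| 20°C | about 100% | 0.01 / 0.04 | 0.00 / 0.02 |
| 15°C | 93% | 0.14 / 0.38 | 0.37 / 0.97 |
| 10°C | 72% | 0.31 / 0.72 | 0.73 / 1.00 |

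The loss at the coldest point runs from total to modest, depending on T and on the size of the benefit. Under the first set of assumptions the loss of power for the mean over the whole challenge was small; the harm is to the size and timing of the estimated effect.

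Only sensation was modelled. The documents give no basis for saying when comfort would reach 4.

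**The case against.** A reader might infer that the scale cannot show any benefit in the coldest water, or that the late readings will be at the floor in both conditions. The documents do not support either statement. The sentence in Section 9.0 is a risk disclosure in ordinary language; it attaches no temperature, time or rating to the word cold. No section says when a rating of 1 is reached. A placebo rating of 1 against a drug rating of 2 still shows a benefit, so information is lost mainly where both visits sit at 1. Stopping for intolerance or core temperature would also remove some of the readings most likely to be at the limit.

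It can be added that the false interaction assumes a constant benefit, which no section claims; that the comfort scale is a separate instrument; and that readings every 5 minutes can already show a delay in reaching 1. Most important, the Aim 2 primary and secondary outcomes in Sections 3.1, 3.2 and 12.0 concern core temperature and shivering. Thermal perceptions are listed as secondary outcomes only for Aim 1.

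These points stand, and they limit the concern to a risk of uncertain size on a supporting outcome. They do not remove it. In the first simulation the difference at 10°C is attenuated at every assumed T, even when the mean reaches 1 only at 10°C. The delay in reaching 1 can be derived from the data, but the plan does not say it will be analysed.

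**Conclusion.** The concern holds as a risk. The Aim 2 sensation scale has no room below cold, the plan expects cold to be felt, and the stated analysis does not allow for a floor. Where both visits are at 1, the ANOVA on raw ratings would hide or shrink a difference between mirabegron and placebo, and could make a steady benefit appear to fade.

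The size rests almost wholly on an input that the documents do not give. For a constant 0.5-point benefit, the average understatement is about 69% if 1 is reached at 28°C and about 7% if it is reached at 10°C; the difference seen at 10°C ranges from about 0 to 0.32. These figures also depend on the assumed linear decline, the assumed SDs, whole-number ratings and completed challenges.

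The main Aim 2 conclusions do not depend on these ratings. The point is minor to moderate, and worth acting on because the remedy is cheap and detail lost at the limit cannot be recovered after data collection.

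**What to change.** 1. For Aim 2, add sensation categories below cold (for example very cold and extremely cold) and comfort categories beyond very uncomfortable, keeping the existing anchors and their numbers.
2. Whatever scale is used, add to Section 12.0 a comparison between conditions of the water temperature (or time) at the first sensation rating of 1 and the first comfort rating of 4, paired within participant and censored when the rating is not reached. The 5-minute readings locate this to within 1°C of water temperature.
3. State that a null difference, or a condition by time interaction, in readings where both visits are at the scale limit will not be interpreted as absence of perceptual benefit.

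Dropping all readings after either visit reaches the limit is not a good substitute, because it selects readings on the outcome being compared.

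The cost is a revised rating card and a few sentences in the analysis section, with no added visits or measurements. There are two drawbacks. Participants already studied have only the shorter scale; items 2 and 3 still apply to them. The Aim 1 and Aim 2 cards would also differ, although Section 6.0 lets the same person take part in both, and new categories may change how the retained points are used. Raw ratings should therefore not be compared across the two aims without that caution.
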